Per protocol Immunogenicity- Non-vaccinated Neonates/Infants (PPI-NVN)	All NVN born to Ad26.COV2.S vaccinated adult participants for whom immunogenicity data are available excluding neonates/infants born to participants with major protocol deviations that are expected to impact the immunogenicity outcomes (for example missed vaccinations in the mothers), or neonates/infants with major protocol deviations that are expected to impact the immunogenicity outcomes

Population	Description
	The list of major protocol deviations to be excluded from the immunogenicity analyses will be specified in the Major Protocol Deviation Criteria document and/or this list will be reported into the protocol deviation dataset of the clinical database before database lock.

Primary/Secondary Endpoint(s)

Immunogenicity Endpoints

No formal statistical testing of immunogenicity data is planned. Descriptive statistics (geometric mean and confidence intervals, or median and interquartile range Q1-Q3, as appropriate) will be calculated by group and overall, for immunologic parameters for all available time points for adult participants receiving Ad26.COV2.S during the 2nd and/or 3rd trimester of pregnancy.

Descriptive statistics will also be presented for neonates/infants of adult participants who have received Ad26.COV2.S during the 2nd and/or 3rd trimester of pregnancy by group and overall.

Several definitions of serological responses will be applied (fold increases in GMC [S-ELISA] or GMT [VNA]). Graphical representations of immunologic parameters will be prepared as applicable. Frequency tabulations will be calculated for discrete (qualitative) immunologic parameters, as applicable.

The impact of baseline characteristics on the humoral responses may be explored graphically or with descriptive statistics by group and overall.

For adult participants, all immunogenicity analyses will be performed on the PPI-A by group (previous vaccination status) and overall. Immunogenicity analyses may also be performed by stage of pregnancy at which the vaccine was administered, vaccination regimen (ie, 1-dose schedule or 1-dose schedule with a booster dose), SARS-CoV-2 baseline serostatus and by actual vaccine history within each group.

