For neonates/infants, immunogenicity analyses will be performed on the PPI-NVN set by group and overall. Analyses may also be performed by the gestational age at the time of vaccine administration, and SARS-CoV-2 baseline serostatus of the adult participant.

Safety Endpoints

No formal statistical testing of safety data is planned. Safety data will be analyzed descriptively for adult participants (including pregnancy outcomes) and their neonates/infants up to approximately 12 months of age (including neonatal outcomes) for all enrolled participants.

For adult participants, all safety analyses will be performed on the Full Analysis Set-Adults (FAS-A).

For adult participants, safety analyses may also be performed by stage of pregnancy at which the vaccine was administered, vaccination regimen (ie, 1-dose schedule or 1-dose +booster), SARS-Cov-2 baseline serostatus and by actual vaccine history within each group.

For neonates/infants, safety analyses will be performed on the FAS-NVN.

For neonates/infants, analyses may also be performed by vaccination regimen (1-dose schedule or 1-dose +booster) received by the adult participant during the study.

Outcomes

Adverse maternal/fetal outcomes and adverse neonate/infant outcomes will be defined using the Case Definitions for Pregnancy Outcomes for each endpoint.

Planned Analyses***Primary Analysis***

The primary analysis of safety and immunogenicity will be performed when all adult participants have completed the 42-day postpartum visit in all groups (or for participants who discontinued earlier).

The analysis will include safety (AEs, SAEs, AESIs, pregnancy-related AEs throughout pregnancy and pregnancy outcomes) and immunogenicity data (ELISA and VNA) for all adult participants and neonates/infants and in cord blood at the time of delivery. The primary analysis will include all data up to and the Day 42 postpartum follow-up visit (inclusive). The results of this analysis may be used for regulatory submissions.

[figure not shown]
Final Analysis

The final analysis will be performed when all adult participants and all neonates/infants have completed the final visit. Analysis will include safety (AEs, SAEs, and pregnancy outcomes) and immunogenicity data. Booster dose effect will be evaluated on safety and immunogenicity.

Note: Interim analyses may be performed as required or if requested by health authorities.

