6.2. Booster Vaccination

Vaccine Naïve Participants

Vaccine naïve participants at study entry (Group 4, including Sentinel and Safety Cohorts) who have completed the pregnancy during which they were enrolled in the study, are not pregnant again will be offered an (optional) booster vaccination with a single dose of Ad26.COV2.S at 5×10^{10} vp. They must not meet any study discontinuation criteria as specified in Section 7.1 and have not received another COVID-19 vaccine (eg, national immunization program) outside the study as indicated in the SoA in Section 1.3.1.1.

The booster vaccination will be administered not earlier than 2 months after completion of the participant's Ad26.COV2.S vaccination in the study. The booster vaccination and the booster follow-up visit should not extend the study duration.

The Booster Vaccination Visit for vaccine naïve participants at study entry should preferably coincide with a scheduled visit from the original SoA in Section 1.3.1. If not operationally feasible to coincide with an existing visit, an unscheduled visit may be planned.

Participants will continue to follow the Schedule of Activities in Section 1.3.1. All participants (whether they consent to the booster vaccination or not) will be encouraged to remain in the study.

Previously Vaccinated Participants (Group 1-3)

Previously vaccinated participants (Groups 1-3) will receive a single (booster) dose of Ad26.COV2.S at 5×10^{10} vp as part of the study, but are not eligible for a second booster during the study.

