7.2. Delay or Discontinuation of Vaccination due to Pregnancy-Specific Complications

The booster vaccination (Group 4 only) (see Section 6.2) may be withheld or delayed if the participant experiences any of the following pregnancy-specific complications prior to the scheduled booster vaccination:

- severe vaginal bleeding;
- preterm premature rupture of membranes;
- severe pre-eclampsia, eclampsia;
- hemolysis elevated liver enzymes and low platelets (HELLP) syndrome;
- stillbirth;
- fetal loss;

^a Note: Ocular, topical or inhaled steroids are allowed.

- preterm birth;
- participant has a positive diagnostic molecular test result for SARS-CoV-2 infection on the day of the booster vaccination.

In the event that any of the above occurs, the participant (and infant, if applicable) will continue to be followed until the end of the study in accordance with the [Schedules of Activities](#).

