No formal statistical hypothesis for immunogenicity will be tested. Immunogenicity analyses will be performed on the PPI-NVN set. Analyses may also be performed by vaccination regimen received by the infant's mother during pregnancy and the gestational age at the time of vaccine administration and/or by SARS-CoV-2 baseline serostatus of the infant's mother. The effect of homologous and heterologous boosters on binding antibodies and neutralizing antibody titers in neonates born to previously vaccinated mothers will be evaluated descriptively by group and overall.

A secondary objective of the study is to assess antibody levels against SARS-CoV-2 in neonates/infants born to adult participants who have received Ad26.COVS during the 2nd and/or 3rd trimester of pregnancy, at birth (ie, in cord blood) and at approximately 2 months and 6 months, of age by group and overall, using ELISA (S-ELISA, EU/mL and GMCs).

A further secondary objective of the study is to assess antibody levels against SARS-CoV-2 in neonates/infants born to adult participants who have received Ad26.COVS during the 2nd and/or 3rd trimester of pregnancy, at birth (ie, in cord blood), as measured by VNA titers (antibody GMTs) by group and overall.

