9.4.1. General Considerations

Analysis populations are defined in Section 9.3.

Primary and final analyses are defined in Sections 9.5.1 and 9.5.2.

No formal statistical testing of safety or immunogenicity data is planned. Safety and immunogenicity will be summarized with descriptive statistics by group and overall. Safety and immunogenicity analyses may also be performed by stage of pregnancy (16-27 weeks, 28-38 weeks), administration of booster (Yes, No), SARS-CoV-2 baseline serostatus (Positive, Negative) at which the vaccine was administered and by actual vaccine history within each group.

For adult participants, all safety analyses will be performed on the FAS-A and immunogenicity analyses will be performed on the PPI-A by group and overall.

For neonates/infants, safety analyses will be performed on the FAS-NVN and immunogenicity analyses will be performed on the PPI-NVN set by group and overall.

The number and percentage of participants screened, enrolled, vaccinated, received a booster vaccine and completed follow-up will be summarized by group and overall.

Baseline is considered as the last available assessment before vaccination. For neonates baseline is value at birth.

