9.5.2. Final Analysis

The final analysis will be performed when all adult participants and all neonates/infants have completed the final visit per the Schedules of Activities in Section [1.3](#). Analysis will include safety (AEs, SAEs, and pregnancy outcomes) and immunogenicity data. Booster dose effect will be evaluated on safety and immunogenicity.

The SAP will describe the planned analyses in greater detail.

Note: Interim analyses may be performed as required or if requested by health authorities.

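### Optional splits by the mother's postpartum booster cover outcomes that precede the booster and may decide who receives it

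*Protocol*

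**What the plan says.** The synopsis, under Primary/Secondary Endpoint(s), offers booster status as an optional subgroup factor three times:

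- adult immunogenicity, by "vaccination regimen (ie, 1-dose schedule or 1-dose schedule with a booster dose";
- adult safety, by "vaccination regimen (ie, 1-dose schedule or 1-dose +booster), SARS-Cov-2 baseline serostatus and by actual vaccine history within each group";
- infant safety: "For neonates/infants, analyses may also be performed by vaccination regimen (1-dose schedule or 1-dose +booster) received by the adult participant during the study".

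Section 9.4.1 repeats it for safety and immunogenicity, listing "administration of booster (Yes, No), SARS-CoV-2 baseline serostatus (Positive, Negative" among the possible factors. Section 9.2.1 does the same for adult immunogenicity. All of these are worded as permitted, not required, and all analyses are descriptive. Section 9.5.2 is firmer on the booster in general: "Booster dose effect will be evaluated on safety and immunogenicity".

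Section 6.2 offers the optional booster only to Group 4 women "who have completed the pregnancy during which they were enrolled in the study", no sooner than 2 months after the study dose. Section 1.3.1.2, footnote a, allows it up to 11 months after birth. Groups 1-3 cannot receive a further dose. Section 7.2 says the booster "may be withheld or delayed if the participant experiences any of the following pregnancy-specific complications prior to the scheduled booster vaccination"; its list includes preterm birth, stillbirth, fetal loss and severe pre-eclampsia. Section 7.1 requires study vaccination to stop after a related SAE or Grade 4 event.

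For infant immunogenicity, Section 9.2.1 uses a different regimen definition: what was received by the infant's "mother during pregnancy and the gestational age at the time of vaccine administration".

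**The concern.** The label separating 1-dose from 1-dose plus booster is settled after delivery, and partly by how the pregnancy went. The sentences that permit the split set no landmark, do not restrict it to Group 4, and do not limit it to events after the booster. Read as written, they allow tables of preterm birth, low birth weight, Day 29 antibody or AEs after dose 1 by a dose given later. The boosted column would then be filtered towards uncomplicated pregnancies. A reader could take the contrast for a booster effect, or for reassurance about safety, when the booster could not have influenced those endpoints. Because nothing is tested, the harm is a misleading descriptive table, not an inflated error rate.

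**Working it through.** The plan states no figure for this contrast, so there is none to reproduce. The check covers timing, dependence and size.

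**1. Timing.** The booster comes at the earliest 2 months after dose 1 and after the pregnancy ends (6.2), and at the latest 11 months after birth (1.3.1.2).

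- Preterm birth, stillbirth, low birth weight, small for gestational age and congenital anomalies are fixed at or before birth, hence before any booster.
- The Day 29 sample has a window of 7 days, so it falls by Day 29 + 7 = Day 36, before 2 months.
- The 7-day solicited and 28-day unsolicited AE collection periods after dose 1 also end before 2 months (solicited events may be followed to resolution).
- Adult SAEs, suspected AESIs and MAAEs, and infant SAEs and MAAEs, can fall on either side of the booster. If it is given 1.4, 6 or 11 months after birth, then 1.4/12 = 12%, 6/12 = 50% or 11/12 = 92% of the infant's 12-month follow-up has already passed.

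**2. Dependence.** Section 7.2 links the booster to pregnancy outcome and Section 7.1 links it to related SAEs and Grade 4 events. Boosted women must also be ongoing, consenting, not pregnant again and without an outside COVID-19 vaccine. No rule ties the booster to antibody level, so for Day 29 antibody the split is chiefly uninformative, with any selection indirect. An unrestricted split also places all of Groups 1-3 in the 1-dose category, which mixes booster status with prior vaccination.

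**3. Size, for preterm birth with no booster effect.** Inputs:

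- p = 8.9%, the background preterm rate quoted in Section 2 (a general population figure, not this trial's);
- u = share of otherwise eligible women boosted, assumed 0.3 to 0.8;
- w = chance that a preterm case who would have been boosted ends the study unboosted, assumed 0 to 1. A booster that is only delayed counts as w = 0.

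Formulas:

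- boosted rate = p·u·(1−w) / [p·u·(1−w) + (1−p)·u]
- unboosted rate = p·[1−u·(1−w)] / {p·[1−u·(1−w)] + (1−p)·(1−u)}

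At u = 0.5, w = 1: boosted 0%; unboosted 0.089 / (0.089 + 0.4555) = 16.3%.

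At u = 0.5, w = 0.5: boosted 0.02225 / (0.02225 + 0.4555) = 4.7%; unboosted 0.06675 / (0.06675 + 0.4555) = 12.8%.

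| u | w | boosted | unboosted | gap (points) |
|---|---|---|---|---|
| 0.3 | 0.5 | 4.7% | 10.6% | 5.9 |
| 0.3 | 1 | 0% | 12.2% | 12.2 |
| 0.5 | 0 | 8.9% | 8.9% | 0 |
| 0.5 | 0.5 | 4.7% | 12.8% | 8.1 |
| 0.5 | 1 | 0% | 16.3% | 16.3 |
| 0.8 | 0.5 | 4.7% | 22.7% | 18.0 |
| 0.8 | 1 | 0% | 32.8% | 32.8 |

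**4. Numbers at hand.** Group 4 holds at least the 22 Sentinel and Safety Cohort women, against a target of at least 25. At 8.9% that gives 22 × 0.089 = 2.0 to 25 × 0.089 = 2.2 expected preterm births, so one or two withheld boosters would settle the contrast.

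**The case against.** The strongest reply is that these tables are optional and that the protocol already evaluates the booster sensibly elsewhere. The firm analyses are by group and overall. With enrolment stopped, Section 9.4 says some endpoints may only be listed. Booster safety endpoints are anchored to the booster date (7 days solicited, 28 days unsolicited), and booster immunogenicity is pre-boost against post-boost. Section 9.4.2 leaves booster status out of its subgroup lists and allows a separate descriptive safety analysis of boosted women. It also summarises adult SAEs, suspected AESIs and discontinuation AEs by phase, including post booster. Risk windows for optional subgroups are normal SAP content.

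Most of this stands, and it rules out several stronger readings:

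- A reader might infer that the splits are mandated. They are not; only evaluation of the booster effect in general is firm.
- A reader might infer that the synopsis and Section 9.2.1 flatly contradict each other on infant regimen. The synopsis sentence concerns safety and the Section 9.2.1 sentence immunogenicity. The wordings differ and should be reconciled, but they govern different endpoints.
- A reader might infer that the booster can affect no infant outcome. That holds for outcomes fixed at birth. Infant safety runs to about 12 months, and breast milk is sampled around the booster, so infant events after it are a fair question.

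What does not stand is that optional wording cures the problem. The permitted split reaches endpoints for which it has no valid interpretation, and the by-phase safeguard covers adults only.

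**Conclusion.** The point holds in a limited form. The synopsis and Sections 9.2.1 and 9.4.1 permit descriptive splits by a factor that follows, and may depend on, some of the endpoints being split. For pregnancy and birth outcomes, Day 29 antibody and AEs in the early windows after dose 1, such a split says nothing about the booster and can show a spurious difference.

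Its size cannot be fixed from the protocol. At 8.9% preterm and no booster effect, the gap is 5.9 to 32.8 percentage points over uptake of 0.3 to 0.8 and withholding of 0.5 to 1; it is nil by this route if withholding never occurs and uptake is unrelated to outcome. Uptake and withholding are assumptions. The 8.9% may be high here, since high-risk and multiple pregnancies are excluded and women enrolled very late cannot deliver preterm. It would therefore be wrong to infer that the tables are certain to favour the booster. Nor does the boosted group exclude women with ordinary reactogenicity: the vaccine-reaction grounds in Section 7.1 are anaphylaxis and related serious or Grade 4 events. Nothing here questions the clinical withholding rules themselves.

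**What to change.** - In the synopsis and Sections 9.2.1 and 9.4.1, exclude from the booster split all pregnancy outcomes, neonatal outcomes fixed at or before birth, and any adult endpoint measured before the booster.
- Evaluate the booster only within Group 4 and only on time after it: antibody from pre-boost to 28 days post-boost, and post-booster AEs by phase. Limit any infant safety comparison to events after the mother's booster or after a stated landmark.
- Align the synopsis and Section 9.4.1 with Section 9.4.2, which already omits booster status from its subgroup lists.
- Reconcile the infant regimen wording in the synopsis and Section 9.2.1, stating which endpoint each definition serves. Simply adopting the Section 9.2.1 definition would not do: every mother received one dose in pregnancy, so it gives a single category, and it would also drop legitimate infant follow-up after the booster.

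The cost is protocol and SAP wording and a few optional tables. No new data, visits or participants are needed.

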1.2. Schema

Figure 1: Schematic Overview of the Study

Monthly phone calls are intended for safety follow up and delivery planning, should start after Day 29 and continue periodically until birth.

For the main study, the aim is to recruit at least 40 participants in Groups 1-3 and at least 25 participants in Group 4. All these participants will receive a single dose of Ad26.COVS.2.S at 5x10¹⁰ vp.

A booster vaccination with a single dose of Ad26.COVS.2.S at 5x10¹⁰ vp will be offered to ongoing, consenting participants who were vaccine naïve at study entry (Group 4, including Sentinel and Safety Cohorts), and who have completed the pregnancy during which they were enrolled in the study, are not pregnant again and have not received another COVID-19 vaccine (eg, national immunization program). If a booster is administered in these participants, the postpartum and booster visits can be combined.

1.3. Schedules of Activities

1.3.1. Adult Participants: Group 4: (Including Sentinel and Safety Cohorts)

Phase ^a	Screening ^a	Study Period					Birth	Follow-up				
Visit ^b	1	2 ^g	3	4	5	6-8*	9	10	11	12 ^{ee}	EE ^c	
Visit Timing		Dose 1	Dose 1 + 7d	Dose 1 + 14d	Dose 1 + 28d	Monthly phone calls after Dose 1 + 28 days	Pregnancy completion/ termination	PP 1 + 42d	PP 1 + 6 m	PP 1 + 12 m End of Study	Early Exit	
Visit Day and (Window)	-28 to 1	D1	D8 (±3d)	D15 (±3d)	D29 (±7d)		PP 1 ^d (-1 to +3d)	PP 43 (±14d)	PP 183 (±14d)	PP 366 (±14d)		
Visit Type	Screening	Vaccination	Safety	Safety	Safety Immuno	Phone Call for Safety follow-up	Safety Immuno	Safety Immuno	Safety Immuno	Safety	Early exit	
Informed consent (ICF) ^a	●											
Inclusion/exclusion criteria	●	● ^{1,f}										
Randomization		● ¹										
Demographics ^g	●											
Medical and obstetric history ^h ; pre-pregnancy and prestudy meds	●	● ¹										
History of COVID-19 vaccination ^{bb}	●											
Full physical examination ^h	●	● ¹									●	
Obstetric examination ^h	●	● ¹									●	
Targeted physical examination ^h			●	●	●		●	●	●	●		
Vital signs including body temperature ^{aa}	●	● ²	●	●	●		●	●	●	●	●	
Pulse oximetry ^d		● ¹										
Obstetric ultrasound ^k	●	● ¹									●	
Nasal swab sample and test for SARS-CoV-2 RNA ^l	● ³	● ^{1,4}										
Pre-vaccination symptoms ^m		● ¹										
eCOA training and set-up ⁿ		● ¹										
Distribution of rulers and thermometers		●										
Distribution of pulse oximeter ^o		●										
Training and distribution: nasal swab kit ^{oo}		●										
Symptoms of Infection with Coronavirus-19 (SIC), including highest body temperature measured by the participant (ePROs to be completed by the participant in the eCOA) ^p		● ¹										
Vaccination		●										
30 minutes (60 minutes for the Safety Cohorts) post-vaccination observation ^q		●										
Solicited AE collection ^r		-----Continuous-----										

Phase ^a	Screening ^a	Study Period					Birth	Follow-up			
Visit ^b	1	2 ^c	3	4	5	6-8 ^c	9	10	11	12 ^{ee}	EE ^c
Visit Timing		Dose 1	Dose 1 + 7d	Dose 1 + 14d	Dose 1 + 28d	Monthly phone calls after Dose 1 + 28 days	Pregnancy completion/ termination	PP 1 + 42d	PP 1 + 6 m	PP 1 + 12 m End of Study	Early Exit
Visit Day and (Window)	-28 to 1	D1	D8 (±3d)	D15 (±3d)	D29 (±7d)		PP 1 ^d (-1 to +3d)	PP 43 (±14d)	PP 183 (±14d)	PP 366 (±14d)	
Visit Type	Screening	Vaccination	Safety	Safety	Safety Immuno	Phone Call for Safety follow-up	Safety Immuno	Safety Immuno	Safety Immuno	Safety	Early exit
Investigator's assessment of reactogenicity (participant's diary)			● ⁵								
Unsolicited AE collection ^f		-----Continuous-----									
Investigator's assessment of reactogenicity (participant's diary)			● ⁵								
(Suspected) COVID-19 surveillance (symptom check) ^g		-----Continuous-----									
Adverse maternal, fetal outcomes		-----Continuous-----									●
AE/SAE/AESI/MAAE recording ^h		-----Continuous-----									●
Concomitant medications ⁱ		-----Continuous-----									●
Delivery history ^j							●				
Safety Sampling											
Laboratory assessments, ~ 6.5 mL ^k	● [#] (~6.5 mL)	● ¹ (~6.5 mL)	● (~6.5 mL)	● ^{cc} (~6.5 mL)	● ^{cc} (~6.5 mL)		● (~6.5 mL)	● (~6.5 mL)			
Whole blood, 12.5 mL ^w Sample will be separated: Plasma sample, 5 mL ^w , Serum, 7.5 mL ^w		● ¹ (5 mL), (7.5 mL)	● (5 mL), (7.5 mL)		● (5 mL), (7.5 mL)		● (5 mL), (7.5 mL)	● (5 mL), (7.5 mL)			
Other sampling											
Humoral immunogenicity sample (serum) ^l		● ¹ (10 mL)			● (10 mL)		● (10 mL)		● (10 mL)		
N-serology sample		● ¹ (2.5 mL)			● (2.5 mL)		● (2.5 mL)		● (2.5 mL)		
Colostrum and breast milk sample, mL (optional) ⁿ							● colostrum 0.5 mL	● breast milk, ≥5 mL			
Vaccination-related biomarker blood sample (PAXgene [®] tubes, 2.5 mL)		● ¹ (2.5 mL)			● (2.5 mL)		● (2.5 mL)				
Cellular immunity (PBMC) blood draw Subset of approximately 25 participants per group, if feasible (optional) ^{dd}		● ¹ (30 mL)			● (30 mL)		● (30 mL)				

Monthly phone calls are intended for safety follow up and delivery planning, should start after Day 29 and continue until birth; #optional laboratory assessments at screening to be done at the discretion of the investigator.

¹ pre dose; ²pre and post dose; ³Screening diagnostic tests for current SARS CoV 2 infection can be performed. ⁴SARS CoV 2 test is to be repeated pre vaccination on Day 1 only if the test at screening was not done or was done more than 4 days before Day 1 visit. ⁵ local and systemic solicited AEs should be verified and reported in eDC according to the toxicity

grading scale. If an event is ongoing 7 days post vaccination, the participant should be encouraged to continue filling in the diary until resolution and the rest of the diary may be reviewed again at the next visit.

Footnotes:

- a. Screening can be performed within 28 days prior to the study vaccination or on the day of vaccination. If screening is performed on the day of vaccination (recommended), Visit 1 and Visit 2 will coincide on Day 1. In that case, laboratory assessments should only be done once. During the screening visit, at least, all eligibility criteria must be verified prior to randomization and vaccination.
- b. If allowed by local regulations: study visits may take place at the participant's home or other location in the event of an ongoing SARS CoV 2 infection performed; visits can be performed by a trained health care professional (HCP) via phone call or a telemedicine contact.
- c. For those participants who are unable to continue participation in the study until the end of study visit, but for whom consent is not withdrawn, an early exit visit will be conducted as soon as possible. Participants who wish to withdraw consent from participation in the study will be offered an optional visit for safety follow up. For these participants only the safety assessments of the early exit visit (no blood sampling for immunogenicity) will be performed.
- d. Postpartum (PP) 1 refers to the day of pregnancy completion/termination. Visit 9 (PP 1) should occur on the day of pregnancy completion/termination or within 3 days after pregnancy completion/termination. Assessments collected the day before birth can be used, but are preferably collected on the date of birth. If the delivery takes place in a hospital where the site staff does not have privileges, it is expected that medical records are obtained to collect the applicable protocol required safety information. Blood samples are not expected in this case.
- e. Signing of the ICF should be done before any study related procedure. The ICF can be signed remotely prior to the Screening Visit. By signing the main ICF, consent is also given to follow up the neonates/infants after birth. Note: Logistics such as downloading of an application to the participant's eDevice, or accessing study materials for enrollment, are not considered a study related procedure.
- f. Check clinical status again before study vaccination.
- g. Maternal demographic information to be collected at screening includes age, race/ethnicity, and geographical location/residence.
- h. Information to be collected for medical and obstetric history, physical examinations and vital signs is specified in Section 8.2. Only relevant medical history (general and obstetric) is to be collected, in particular: history of congenital abnormalities, history of cancer, history of immunodeficiency or conditions treated with immunomodulators, major psychiatric illness, major cardiovascular or lung diseases, history of an allergy to vaccination, ongoing relevant comorbidities per investigator's judgement, history of any comorbidities known to be associated with an increased risk of progression to severe COVID 19 (see Section 10.9), and history of hepatitis B or hepatitis C infection.
- i. Baseline pulse oximetry measurements will be used to estimate the amount of oxygen in the blood, low levels may indicate either SARS CoV 2 infection or an underlying medical condition.
- j. For laboratory assessments, including chemistry and hematology assessment of platelet counts see Appendix 2, Table 6 for details. If the data obtained from the laboratory assessment shows abnormal results that are considered clinically significant, then additional blood samples could be taken until normalization of the readings, at the discretion of the investigator. Urine dipstick for protein and glucose will be performed at these visits. If urinalysis results are positive additional work up for pre eclampsia or gestational diabetes may be warranted, but do not preclude inclusion in the study.
- k. See Section 8.2.1 for details on obstetric ultrasound. Ultrasound is not required at Visit 2 if screening (Visit 1) ultrasound has been obtained within the past 10 days and there is no other indication for repeating the ultrasound (eg, fetal abnormalities).
- l. Diagnostic molecular RT PCR test for SARS CoV 2 infection will be performed at a local laboratory. Test failures or tests that are indeterminate must be repeated. For exploratory endpoint purposes, a molecular RT PCR test for SARS CoV 2 infection may be performed at a central laboratory and will not be reported to the sites. In case of a positive nasal swab result at screening or D1, an exclusion criterion has been met, and samples will not be shipped to central laboratory.
- m. The investigator must check for acute illness or body temperature $\geq 38.0^{\circ}\text{C}/100.4^{\circ}\text{F}$ at the time of vaccination. If any of these events occur within 24 hours prior to the planned vaccination, the vaccination can be rescheduled in accordance to the protocol's window. For further details refer to Section 5.5.
- n. Site staff should provide training to participants to complete the reactogenicity diary using the eCOA on their own eDevice (smartphone or tablet) when feasible, provisioned devices will be available on a limited basis. If a participant is unable to complete the eCOA, a study staff member can collect the information on the participant's behalf as detailed in Section 8.1.2. eCOA set up should be completed before any tests, procedures, to avoid influencing participant responses.
- o. On Day 1, all participants will be provided a pulse oximeter (to measure blood oxygen saturation and pulse rate), thermometer and a nasal swab kit to be used in case of a COVID-19 episode (see Section 8.1.2). The pulse oximeter and thermometer for the neonate/infant can also be provided.
- p. The SIC questionnaire asks the participant if she had any of the prespecified signs or symptoms of COVID 19 (see Section 10.8 Appendix 8) during the past 24 hours (including highest temperature in the last 24 hours), and (when applicable) to rate the severity. The baseline SIC questionnaire (Visit 2) must be completed prior to vaccine administration.

- q. Participants will be closely observed at the site for a minimum of 30 minutes (60 minutes for Sentinels and participants in the Safety Cohort) post vaccination. Sentinels and participants in the Safety Cohort will be vaccinated at least 1 hour apart.
- r. Solicited AEs (reactogenicity) and unsolicited AEs will be assessed from time of vaccination until 7 days post vaccination and 28 days post vaccination, respectively.
- s. Participants will be asked at least twice a week, through the eCOA, if they have experienced any new symptoms or health concerns that could be related to infection with SARS CoV 2. Refer to Section 1.3.4 Procedures for Participants with (Suspected) COVID 19. In addition, participants will be asked daily within the 30 day time period post vaccination if they have experienced any health concerns related to suspected AESI's, and if so, participants will be advised to contact the study center. Refer to Section 8.3.6 Adverse Events of Special Interest.
- t. All SAEs related to study procedures or non investigational sponsor products will be reported from the time a signed and dated ICF is obtained until the end of the study/early withdrawal. MAAE are to be reported for all participants from the moment of the vaccination until 6 months after vaccination. MAAEs leading to study discontinuation which are to be reported until completion of the participant's last study related procedure. New onset of chronic diseases will be collected as part of the MAAEs. See Section 8.3.1 for more details.
- u. Refer to Section 6.8 for collection and recording of concomitant therapies.
- v. Information to be collected for delivery history.
- w. Blood volume will be divided into plasma and serum as described in the laboratory manual and stored for potential coagulation and/or hematology related testing in a central laboratory (see Section 10.2, Appendix 2, Table 7). Unused samples may be used for immunogenicity testing.
- x. Approximately 0.5 mL of colostrum should be collected within 1 week postpartum and approximately ≥ 5 mL of breast milk around PP43. Collection of breast milk and colostrum is optional. Whether the adult participant is breastfeeding, and until when, will be recorded.
- y. A booster vaccination with a single dose of Ad26.COV2.S at 5×10^{10} vp will be offered to ongoing, consenting participants who were vaccine naïve at study entry (Group 4, including Sentinel and Safety Cohorts) and who have completed the pregnancy during which they were enrolled in the study, are not pregnant again (as specified in Section 1.3.1.1) under the conditions delineated in Section 6.2. The booster vaccination will be administered not earlier than 2 months after the participant's Ad26.COV2.S vaccination in the study. The Booster Vaccination Visit should preferably coincide with a scheduled visit. If not operationally feasible to coincide with an existing visit, an unscheduled visit may be planned. After the booster vaccination and 28 day post booster visit, participants will continue procedures and visits as in the original SoA.
- z. In the situation of a completion/ termination of the pregnancy before the completion of the applicable Study Period visits, PP1 (Visit 9) is to be completed. The participant should then follow the visits scheduled in the 'Study Period' up to Visit 5 (meaning all scheduled visits in this period except for the monthly phone calls Visits 6 8) AND the 'Follow up' section of the schedule of activities (Visits 10 12). Additional guidance if the pregnancy is completed/ terminated before the pre partum visits are completed is provided in Appendix 10.13.
- aa. Body temperature will be measured preferably via the oral route, or in accordance with the local standard of care.
- bb. History of COVID 19 vaccination (name/manufacturer of the vaccine and date of administration) ≥ 4 months prior to the study vaccine will be reported in the eCRF.
- cc. Laboratory assessments performed at Visits 4 and 5 are optional. If the outcome from the laboratory assessment at Visit 3 show abnormal results that are considered clinically significant, then an on site visit should be performed. In this case, an additional sample should be taken for further assessment 7 days later and until normalization of the readings, at the discretion of the investigator and targeted physical examinations and vital signs should be collected. If the outcome from the laboratory assessment at Visit 3 show normal results, only a safety phone call is required (no physical examinations and vital signs needed).
- dd. With only 1 participant in this subset at the time of writing this Protocol Amendment 7, PBMC sampling will be removed from the study as of Protocol Amendment 7 approval.
- ee. The Follow up safety assessments for adults at the end of the study visit (no.12) may be performed simultaneously with postnatal (PN 12 months) follow up safety visit (no. 14) as feasible.

AE adverse event; AESI adverse event of special interest; COVID 19 coronavirus disease 2019; d day(s); eCOA electronic clinical outcome assessment; eDC electronic data capture; FU follow up; ICF informed consent form; MAAE medically attended adverse event; m months; PBMC peripheral blood mononuclear cell; PP postpartum; SAE serious adverse event; SIC Symptoms of Infection with Coronavirus 19; SARS CoV 2 severe acute respiratory syndrome coronavirus2.

1.3.1.1. Vaccine Naïve Adult Participants (Group 4, Including Sentinel and Safety Cohorts): Booster Vaccination Visits

Participants who are vaccine naïve at study entry will be offered an (optional) booster vaccination with a single dose of Ad26.COV2.S at 5×10^{10} vp.

The booster will be offered (as outlined in Section 6.2) to:

1. Group 4 participants, including Sentinel and Safety Cohorts,
2. Participants who are ongoing and consenting,
3. Participants who have completed the pregnancy during which they were enrolled in the study, are not pregnant again,
4. Participants have not received another COVID-19 vaccine (eg, national immunization program), and
5. Participant does not meet any criterion per section 7.1 (Discontinuation of Study Vaccination)

Previously vaccinated participants (Groups 1-3) will receive a single dose of Ad26.COV2.S at 5×10^{10} vp as part of the study, but are not eligible for a second booster during the study.

1.3.1.2. Vaccine Naïve Adult Participants (Group 4, Including Sentinel and, Safety Cohorts): Booster Vaccination Schedule

Visit #	Booster Vaccination Visit PB 1 ^a	PB 1 + 28d ^b
Visit Timing and Window	No earlier than Vac1 + 2 months	PB 29 (±7d)
Informed consent ^c	● [#]	
Vital signs including body temperature ^d	● [#]	
Pulse oximetry	● [#]	
Pre-vaccination symptoms ^c	● [#]	
Targeted physical examination ^f	● [#]	●
Urine pregnancy test	● [#]	
Blood sample for humoral immunogenicity (serum), mL ^g	● [#] 10 mL	●10 mL
N-serology ^g	● [#] 2.5 mL	●2.5 mL
Vaccination-related biomarker blood sample (PAXgene [®] tubes, 2.5 mL)	● [#] 2.5 mL	●2.5 mL
Colostrum (≥0.5 mL)/ Breast milk sample (≥5mL) (optional) ⁿ	●	●
Clinical laboratory blood sample (whole blood) ^{g,h}	● [#] 15 mL	●15 mL
Vaccination	●	
30 minutes post-vaccination observation	●	
Solicited AE recording ⁱ	●	
Investigator's assessment of reactogenicity (participant's diary)		● ⁺
Breast milk production changes ^p	●	●
Unsolicited AE recording ⁱ	●	
(Suspected) COVID-19 surveillance (symptom check) ^k	-----Continuous-----	
AE/SAE/MAAE/AESI recording ^l	-----Continuous-----	
Concomitant therapies ^m	● ^o	●

[#] Procedure to be completed pre-vaccination

- The booster vaccination will be administered not earlier than 2 months after completion of the participant's Ad26.COVS.2.S vaccination in the study and should be administered latest at birth +11 months. The study duration will not be extended. (See Section 6.2).
- After the Booster Vaccination Visit, participants will resume procedures and visits depicted in Schedule of Activities, Section 1.3.1.
